7.2. Assessment of Adverse Events and Serious Adverse Events

The investigator or qualified sub-investigator is responsible for assessing AEs and SAEs for causality and severity, and for final review and confirmation of accuracy of event information and assessments.

7.2.1. Assessment of Causality for Idelalisib and Procedures

The investigator or qualified sub-investigator is responsible for assessing the relationship to idelalisib therapy using clinical judgment and the following considerations:

- **No:** Evidence exists that the adverse event has an etiology other than idelalisib. For SAEs, an alternative causality must be provided (eg, pre-existing condition, underlying disease, intercurrent illness, or concomitant medication).
- **Yes:** There is reasonable possibility that the event may have been caused by the investigational medicinal product.

It should be emphasized that ineffective treatment should not be considered as causally related in the context of adverse event reporting.

The relationship to study procedures (eg, invasive procedures such as venipuncture or biopsy) should be assessed using the following considerations:

- **No:** Evidence exists that the adverse event has an etiology other than the study procedure.
- **Yes:** The adverse event occurred as a result of protocol procedures, (eg., venipuncture)

7.2.2. Assessment of Severity

The severity of AEs will be graded using the CTCAE, Version 4.03 and available at:
http://evs.nci.nih.gov/ftp1/CTCAE/CTCAE_4.03_2010-06-14_QuickReference_8.5x11.pdf

If a CTCAE criterion does not exist, the investigator should use the grade or adjectives: Grade 1 (mild), Grade 2 (moderate), Grade 3 (severe), Grade 4 (life-threatening), or Grade 5 (fatal) to describe the maximum intensity of the adverse event. For purposes of consistency with the CTCAE, these intensity grades are defined in [Table 7-1](#).

Table 7-1. Grading of Adverse Event Severity

Grade	Adjective	Description
Grade 1	Mild	Sign or symptom is present, but it is easily tolerated, is not expected to have a clinically significant effect on the subject's overall health and well-being, does not interfere with the subject's usual function, and is not likely to require medical attention.
Grade 2	Moderate	Sign or symptom causes interference with usual activity or affect clinical status, and may require medical intervention.
Grade 3	Severe	Sign or symptom is incapacitating or significantly affects clinical status and likely requires medical intervention and/or close follow-up.
Grade 4	Life-threatening	Sign or symptom results in a potential threat to life.
Grade 5	Fatal	Sign or symptom results in death.

The distinction between the seriousness and the severity of an adverse event should be noted. Severe is a measure of intensity; thus, a severe reaction is not necessarily a serious reaction. For example, a headache may be severe in intensity, but would not be classified as serious unless it met one of the criteria for serious events listed in [Section 7.1.2](#).

7.3. Evaluation, Intervention, and Drug Discontinuation for Specific Adverse Events or Conditions

7.3.1. Dermatological Events (Idelalisib)

Subjects receiving idelalisib with \geq Grade 3 rash have generally presented with a maculopapular rash on the trunk and extremities that is occasionally associated with fever and/or pruritus and responded to treatment with diphenhydramine and/or topical or oral corticosteroids.

For subjects who develop Grade ≥ 3 rash for which an underlying etiology cannot be identified (e.g., infection, co-suspect drug), study drug must be interrupted. Severe cutaneous reactions, including fatal events of Stevens-Johnson syndrome (SJS) and toxic epidermal necrolysis (TEN), have been reported in subjects receiving idelalisib. Assessment of potential causal association between idelalisib and the occurrence of SJS or TEN has been confounded by the coadministration of antineoplastic agents (e.g., bendamustine, rituximab) and/or other concomitant medications known to be associated with SJS or TEN (e.g., allopurinol). If SJS or TEN is suspected, idelalisib and all coadministered medications associated with SJS or TEN should be interrupted and the subject treated accordingly.

Subjects should be monitored for the development of SJS, TEN, or other severe cutaneous reactions and idelalisib treatment should be discontinued if such events occur.

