5.2.9. Dose Levels

Idelalisib dose levels are shown in [Table 5-1](#). The starting dose level will be 150 mg BID. The lower dose level (Dose Level -1) is provided in case a subject requires a dose modification.

Table 5-1. Idelalisib Dose Levels

Dose Level	Dosing Regimen
Starting	150 mg BID
-1	100 mg BID

Abbreviation: BID=twice per day

Consistent with [Table 5-2](#), if a subject experiences an AE that is suspected to be related to idelalisib during the course of study, idelalisib administration may be held, as necessary, until the AE resolves or stabilizes to an acceptable degree (as defined in [Table 5-2](#)). Thereafter, idelalisib may be reinitiated at either the Starting Dose Level or at Dose Level -1 consistent with the instructions in Section [5.2.10](#). A further attempt at reinitiation of therapy at Dose Level -1 may be attempted if the investigator feels that a second rechallenge at that dose level is medically appropriate. If the subject cannot tolerate idelalisib after 2 rechallenges at Dose Level -1 for the same AE, then the subject should be discontinued from idelalisib treatment.

After an idelalisib dose reduction, the dose need not be re-escalated, even if there is minimal or no toxicity with the reduced dose. However, if the subject tolerates Dose Level -1 of idelalisib for \geq 4 weeks, then the dose may be increased back to Starting Dose Level, at the discretion of the investigator. Such a re-escalation may be particularly warranted if further evaluation reveals that the AE that led to the dose reduction was not related to idelalisib.

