5.2.10. Idelalisib Dose Adjustments

The dose adjustment recommendations and requirements in [Table 5-2](#) are based on the Common Terminology Criteria for Adverse Events (CTCAE) grade of specific toxicities. However, exceptions are expected for subjects who initiate study treatment with low blood counts. Clinical judgment should apply, and in cases of uncertainty, the study medical monitor should be contacted.

The dose modification instructions in [Table 5-2](#) focus on the types of events most commonly associated with idelalisib. The modifications include both recommended and required actions. When a modification is indicated as a recommendation, it serves as a guideline; variations from the recommendation may be warranted based on an investigator's individual judgment in considering potential risks, benefits, and therapeutic alternatives available to each subject.

Table 5-2. Dose Adjustment Guidelines {Gilead Sciences Inc 2014}

NCI CTCAE Grade ^a	Idelalisib
HEMATOLOGICAL ADVERSE EVENTS	
Neutropenia	
Grade \leq 2 neutropenia	Recommended Action: Maintain current dose level and schedule.
Grade \leq 3 neutropenia	Required Action: Monitor blood counts at least weekly until ANC \leq Grade 2. Recommended Action: Maintain current dose level and schedule.
Grade 4 neutropenia (or occurrence of neutropenic fever or infection)	Required Action: 
Withhold idelalisib.Monitor blood counts at least weekly until ANC \leq Grade 2 Recommended Action: 
May resume idelalisib at lower dose level when ANC grade is \leq Grade 3Neutropenia should be managed according to established clinical guidelines.
Thrombocytopenia	
Grade \leq 3	Recommended Action: Maintain current dose level and schedule.
Grade 4	Required Action: Withhold idelalisib for bruising or bleeding until Grade \leq 3. Recommended Action: May resume idelalisib at initial or reduced dose level at investigator discretion.
NON-HEMATOLOGICAL ADVERSE EVENT	
Rash	
Grade \leq 1	Recommended Action: Maintain current dose level and schedule
Grade 2	Recommended Action: Maintain current dose level and schedule
Grade \geq 3	Required Action: Withhold idelalisib until Grade \leq 1. Recommended Action: Resume at lower dose level or discontinue idelalisib at investigator discretion.
Stevens-Johnson Syndrome (SJS)/Toxic Epidermal Necrolysis (TEN)	

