Grade ≥ 3 diarrhea or colitis or persistent Grade 2 diarrhea or colitis without clear etiology	
Required Action:
 
• Dosing: Withhold idelalisib• Consider anti-diarrheal (eg, loperamide) and/or addition of anti-inflammatory agent (eg, sulfasalazine, budesonide).• Obtain history of onset and duration of diarrhea, including description, number of stools, stool composition (e.g., watery, bloody, nocturnal), travel history, dietary changes and a medication review to identify possible diarrheogenic agents.• Perform physical examination including assessment for fever, dizziness, abdominal pain/cramping, and weakness (e.g., evaluate for sepsis, bowel obstruction, dehydration).• For Grade 3 colitis or diarrhea (unless clinical diagnosis is established from medical history and physical examination), perform stool culture for routine pathogens (Salmonella, Shigella, Campylobacter species, testing for Clostridium difficile toxin, Rotavirus, Cytomegalovirus (CMV), Adenovirus), ova and parasites (Cryptosporidium parvum, Isospora belli, Enterocytozoon bieneusi, Septata intestinalis, Strongyloides, Microsporidia, Entamoeba histolytica, Cyclospora), and Giardia antigen.

NCI CTCAE Grade ^a	Idelalisib
	
Recommended Action:
 
• Dosing: At Grade ≤ 1, may resume at lower dose level or discontinue idelalisib at investigator discretion.• Endoscopy with biopsy is strongly recommended to assess by immunohistochemistry (IHC) and PCR for CMV, Adenovirus PPD• Provide anti-diarrheal agent (eg, loperamide) and maintain current idelalisib dose level and schedule
Hepatic Adverse Events (elevations in ALT, AST, or bilirubin)	
Grade ≤ 1 (ALT/AST $\leq 3\times$ ULN) (Bilirubin $\leq 1.5\times$ ULN)	Recommended Action: Maintain current dose level and schedule.
Grade 2 (ALT/AST $> 3\text{-}5\times$ ULN) (Bilirubin $> 1.5\text{-}3\times$ ULN)	
Recommended Action: Maintain current dose level and schedule
 
Recommended Action: Monitor ALT, AST, ALP, and bilirubin at least 1x per week until all abnormalities are Grade ≤ 1; thereafter, maintain current dose level.

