Grade 3 (ALT/AST $> 5\text{-}20\times$ ULN) (Bilirubin $> 3\text{-}10\times$ ULN)	
Recommended Action: Withhold idelalisib.
 
Required Action:
 
• Monitor ALT, AST, ALP, and bilirubin at least 1x per week until all abnormalities are Grade ≤ 1.• If bilirubin abnormality is Grade < 3, resume idelalisib at same dose level. If bilirubin abnormality is Grade ≥ 3, resume at lower dose level.
Grade 4 (ALT/AST $> 20\times$ ULN) (Bilirubin $> 10\times$ ULN)	
Required Action:
 
• Withhold idelalisib.• Monitor ALT, AST, ALP, and bilirubin at least 1x per week until all abnormalities are Grade ≤ 1.• If bilirubin abnormality is Grade 4, discontinue idelalisib. 
Recommended Action: If bilirubin abnormality is Grade < 4, resume study drug at lower dose level.

Pneumonitis (dyspnea, cough, hypoxia without obvious infectious cause)	
Grade ≤ 1	Recommended Action: Withhold idelalisib until resolution to baseline. May resume at lower dose level or discontinue idelalisib at investigator discretion.
Grade ≥ 2	
Required Action:
 
• Discontinue idelalisib. 
Recommended Action:
 
• Consider bronchoscopy to evaluate for PJP, CMV and other organisms (bacterial and viral)• Consider treatment with systemic corticosteroids.• Consider empiric treatment of pneumocystis if bronchoscopy is contraindicated• Upon resolution, may resume idelalisib at lower dose level at investigator discretion and /Gilead medical monitor agreement

NCI CTCAE Grade ^a	Idelalisib
Pneumocystis jirovecii pneumonia (PJP)	
Any Grade	Required Action: Discontinue idelalisib
Uequivocal CMV infection^c	
Any Grade	Required Action: 
Interrupt idelalisib upon unequivocal clinical or laboratory evidence of CMV infection.Treat according to established clinical guidelines.If the benefits of resuming idelalisib are judged to outweigh the risks, consideration should be given to administering pre-emptive CMV therapy.
Other Nonhematological Adverse Events	
Grade ≤ 2	Recommended Action: Maintain current dose level and schedule
Grade ≥ 3	Recommended Action: Withhold idelalisib until Grade ≤ 1 . May resume idelalisib at initial or lower dose level or discontinue idelalisib at investigator discretion.

a CTCAE, Version 4.03.

b See section [6.2](#) and [7.3.2](#) for additional requirements regarding an AE of diarrhea

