5.3.2. Antibiotics/ PJP Prophylaxis

5.3.2.1. Infectious Events

Patients with lymphoid cancers receiving idelalisib have developed serious and fatal infections during therapy. Opportunistic infections, most notably *Pneumocystis jirovecii* pneumonia (PJP) and CMV infection, have most frequently occurred within the first 6 months of treatment with idelalisib and are increased in the context of concurrent myelosuppressive therapy such as bendamustine.

Subjects must receive trimethoprim-sulfamethoxazole or other established prophylaxis for PJP throughout the course of idelalisib treatment, and for 2 to 6 months following the last dose of idelalisib. Prophylaxis must continue until the CD4+ T-cell count is documented to be >200 cells/mcL after idelalisib treatment ends. Subjects must permanently discontinue idelalisib upon diagnosis of PJP.

CMV surveillance for active disease (quantitative PCR or PP65 antigen) must be conducted approximately every 4 weeks throughout the course of idelalisib treatment. CMV viral load testing should be performed from the same specimen type whenever possible and caution should be exercised when comparing CMV viral load results across different testing centers. If unequivocal clinical or laboratory evidence of CMV infection is present, the subject must interrupt idelalisib treatment and undergo effective antiviral treatment according to established clinical guidelines. If the benefits of resuming idelalisib are judged to outweigh the risks, consideration should be given to administering pre-emptive CMV therapy.

In high-risk subjects (history of recurrent infection, allogeneic transplant, treatment with alemtuzumab, hypogammaglobulinemia) other infection prophylaxis should be considered per consensus guidelines. Administration of intravenous immunoglobulin is permitted per standard institutional practice {[Raanani et al 2009](#)}. For subjects who develop an infection, appropriate medical therapy should be instituted in a timely manner.

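### Section 7.3.1 makes the hold for Grade ≥3 rash narrower than Table 5-2 does, and it stops idelalisib for severe skin reactions that Table 5-2 would let a site restart after

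*Protocol*

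**What the plan says.** **Hold for rash.** Protocol Section 5.2.10, Table 5-2, Rash row, Grade ≥3: "Required Action: Withhold idelalisib until Grade" ≤1. The row sets no condition on cause. Section 7.3.1, second paragraph, deals with the same event but attaches a condition to the mandatory interruption: it applies to Grade ≥3 rash "for which an underlying etiology cannot be identified (e.g., infection, co-suspect drug), study drug must be interrupted".

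**What follows the hold.** After the hold, the Rash row reads "Recommended Action: Resume at lower dose level or discontinue idelalisib at investigator discretion". The row for other nonhematological events at Grade ≥3 recommends (does not require) withholding until Grade ≤1, and then allows either restart, at the initial or a lower dose, or discontinuation.

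**Discontinuation.** Section 7.3.1, third paragraph, says idelalisib should be discontinued for SJS, TEN or other severe cutaneous reactions. It does not define the last term. The row of Table 5-2 that requires discontinuation for a skin event is headed SJS/TEN. The matching bullet in Section 5.5 names SJS, TEN, Grade ≥2 pneumonitis and PJP.

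**General provisions.** Section 5.2.10 opens only the recommended actions to investigator variation and adds that "in cases of uncertainty, the study medical monitor should be contacted". Section 5.5 also has general grounds for stopping: unacceptable toxicity, the subject's best interest, and a benefit-risk balance that the investigator does not judge positive.

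**The concern.** Both texts will be read as instructions. Sections 1.4 and 7.5.2 send the investigator to Table 5-2, while Section 7.3.1 stands under a heading on intervention and drug discontinuation for specific events. Section 7.3.1 does not refer back to the table, and no rule says which text prevails.

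Two situations are left unclear. An investigator who reads only Section 7.3.1 and attributes a Grade ≥3 rash to an infection or another drug finds no mandatory hold there. An investigator who relies on the table after a severe skin reaction other than SJS or TEN finds a permitted restart where Section 7.3.1 says to stop. Section 7.3.1 itself reports fatal SJS and TEN in subjects receiving idelalisib, and says that co-administered drugs confounded the assessment of cause. The hold and stop rules for skin events should therefore be the same wherever they appear.

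**Working it through.** There is no figure to reproduce; the check is a comparison of texts. Four clinical situations cover the ground.

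| Situation | Section 7.3.1 | Table 5-2 | Section 5.5, specific bullet | Do they agree? |
|---|---|---|---|---|
| A. Grade ≥3 rash, no cause found | Must interrupt | Required: withhold until Grade ≤1 | Not addressed | Yes |
| B. Grade ≥3 rash, cause found | No instruction | Required: withhold until Grade ≤1 | Not addressed | 7.3.1 is silent where the table requires a hold |
| C. SJS or TEN | Interrupt if suspected; should discontinue if it occurs | Required: discontinue, any grade | Named | Yes |
| D. Another severe cutaneous reaction | Should discontinue | Rash row or other-nonhematological row: hold, then restart or discontinue | Not named | No: one text says stop, the other permits restart |

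**Situation B.** Section 7.3.1 never says that dosing continues once a cause is found. A site that always withholds complies with both texts. The fault is that the condition makes the mandatory hold in Section 7.3.1 narrower than the Required Action.

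**Situation D.** A site that discontinues also complies with both texts, because each of the two table rows allows discontinuation. A site that restarts stays within the table but departs from Section 7.3.1. The table therefore permits what Section 7.3.1 advises against, and this makes D the sharper of the two points.

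**Boundary between A/B and D.** Table 7-1, which grades events that lack a CTCAE criterion, pairs Grade 3 with the word severe. Since the term in Section 7.3.1 is undefined, a reader could take any Grade 3 rash to be a severe cutaneous reaction that ends treatment, against the Rash row, which allows restart at a lower dose. Any fix has to settle this boundary as well.

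**Exposure.** SAP Section 1.3 reports 3 enrolled subjects; the protocol planned about 6. At most 3 subjects could therefore meet situation B or D. Neither document gives a rate for either event, so no probability is offered.

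**Effect on analysis.** SAP Section 7.1.6 lists all adverse events, and SAP Section 3.5 says no formal testing is done. No result depends on which text a site follows.

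**The case against.** The best defense is that Table 5-2 governs. Only its recommendations are open to variation, so the Required Action for rash stands whatever Section 7.3.1 adds, and dosing through an explained Grade ≥3 rash would mean ignoring it. On discontinuation, Section 5.2.10 says the table concentrates on the commonest events, so Section 7.3.1 is a natural place for rarer ones. Its verb is should, not must. Section 5.5 is a list of reasons for which participation may end, and its general grounds can cover a severe skin reaction. Doubtful cases go to the medical monitor.

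Most of this stands, and it is why the point is minor. It does not remove the mismatch. The general grounds in Section 5.5 rest on the investigator's judgment, and the medical monitor route helps only an investigator who notices that the texts differ.

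A reader might infer more than the documents support:

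- *Section 7.3.1 authorizes continued dosing when a cause is found.* It does not say so; it only fails to repeat the requirement.
- *Section 5.2.9 is a second competing rule, because it speaks of "an AE that is suspected to be related to idelalisib during the course of study, idelalisib administration may be held".* That sentence opens by deferring to Table 5-2 and is permissive. It adds no cause condition to a Required Action.
- *Mandatory PJP prophylaxis gives every subject a ready co-suspect drug.* The protocol allows several agents and does not say that any of them causes rash. The drugs it names as confounders (bendamustine, rituximab, allopurinol) are named in connection with SJS and TEN.
- *Other rows of Table 5-2 show that cause conditions are written in when meant.* In the diarrhea row, "persistent Grade 2 diarrhea or colitis without clear etiology" can be read as qualifying only the Grade 2 part; in the pneumonitis row, the wording on cause belongs to the definition of the event. The contrast is too weak to rely on.

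**Conclusion.** The point holds in two parts. On the hold, Section 7.3.1 is narrower than the Required Action in Table 5-2, although withholding in every case meets both. On discontinuation, Section 7.3.1 advises stopping for severe cutaneous reactions beyond SJS and TEN, while the table rows that would apply permit restart and the Section 5.5 bullet omits them. The conflict with the table carries more weight than the omission from Section 5.5, which is not an exhaustive list (its specific bullet also leaves out bowel perforation, for which Table 5-2 requires discontinuation).

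Severity is minor: an inconsistency in safety instructions for a class of reactions that includes reported deaths, with 3 subjects exposed and no effect on any analysis. The conclusion rests on the current protocol text and on one assumption, that some severe cutaneous reactions are neither SJS nor TEN, which the wording of Section 7.3.1 itself implies. Handling of suspected or diagnosed SJS and TEN is consistent and is not criticized here.

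**What to change.** 1. Section 7.3.1, second paragraph: replace the sentence that carries the etiology qualifier with *For every Grade ≥3 rash, whatever the suspected cause, withhold idelalisib until Grade ≤1 as required in Table 5-2.*
2. Table 5-2, SJS/TEN row, and the matching Section 5.5 bullet: extend both to *SJS, TEN or other severe cutaneous reactions*.
3. Section 7.3.1, third paragraph: keep the term open and give any examples as non-exhaustive. A closed list would send unlisted severe reactions back to rows that permit restart. Add that a Grade 3 rash is not such a reaction by grade alone and follows the Rash row, and that where it is unclear, idelalisib stays withheld and the medical monitor is contacted.

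Section 5.2.9 needs no change. The cost is a few sentences, one row label and one bullet, with the ethics committee approval that Section 9.2.1 requires for any protocol modification. No visits, tests or analyses are added, and the SAP is unaffected.

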7.3.2. Gastrointestinal Events

Isolated cases of gastrointestinal inflammation (eg, stomatitis, colitis, cecitis) have been noted in subjects receiving idelalisib. Rare cases of gastrointestinal perforation have occurred, generally in the setting of occult carcinoma, mesenteric embolus or diverticular disease. Study treatment (idelalisib/placebo) must be discontinued in subjects who experience bowel perforation

Cholangitis manifest as hyperbilirubinemia out of proportion to serum transaminase elevations has been observed. While disease-related factors, neutropenia, toxicity from prior therapies, effects of ongoing supportive care, or pre-existing cholelithiasis may have initiated such events, it is possible that idelalisib played a contributory role. In such subjects, rechallenge with idelalisib has been possible and has not been associated with other severe adverse events. Subjects who have developed evidence of enteritis during idelalisib therapy have been successfully treated with antidiarrheals (eg, loperamide) and with enteric steroid (eg, budesonide) or non-steroidal (eg sulfasalazine [Azulfidine[®]]) anti-inflammatory agents and have been able to continue or resume idelalisib.

[figure not shown]
For study subjects who develop severe abdominal pain the possibility of a bowel obstruction or perforation should be considered. Appropriate clinical and radiographic examination should be performed and supportive care or surgical intervention should be considered. Upon recovery, rituximab may be resumed.

